WHO	World Health Organization

SCHEMA

Title	Prevention of Malaria in HIV-uninfected Pregnant Women and Infants		
Description	Double blinded randomized controlled trial		
Study Objectives 1. To compare the risk of adverse birth outcomes among HIV-uninfected pregnant women randomized to receive monthly SP vs. monthly DP. 2. To compare the incidence of malaria among infants born to mothers randomized to receive IPTp with monthly monthly DP. 3. To validate and adapt a gestational dating by metabolic profile at birth algorithm and to evaluate the added to metabolic profile to identify newborns at increased risk for neonatal death or serious complications.			
Participants and Sample Size	782 HIV-uninfected pregnant women and the children born to them		
Clinical Site	The study will be conducted in Busia District, Uganda. A designated study clinic will be located within Masafu General Hospital. The study clinic will be open daily from 8:00 am to 5:00 pm and after-hours care will be available with the hospital complex.		
Selection Criteria	Inclusion Criteria 1. Pregnancy confirmed by positive urine pregnancy test or intrauterine pregnancy by ultrasound 2. Estimated gestational age between 12-20 weeks 3. Confirmed to be HIV- uninfected by rapid test 4. 16 years of age or older 5. Residency within Busia District of Uganda 6. Provision of informed consent 7. Agreement to come to the study clinic for any febrile episode or other illness and avoid medications given outside the study protocol 8. Plan to deliver in the hospital Exclusion Criteria: 1. 1. History of serious adverse event to SP or DP 2. Active medical problem requiring inpatient evaluation at the time of screening 3. Intention of moving outside of Busia District Uganda 4. Chronic medical condition requiring frequent medical attention 5. Prior SP preventive therapy or any other antimalarial therapy during this pregnancy 6. Early or active labor (documented by cervical change with uterine contractions)		
Treatment assignment	HIV-uninfected pregnant women will be randomized at the time of enrollment		
Treatment arms	Monthly SP Monthly DP		

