6. SUBJECT MANAGEMENT

6.1. Subject Follow-up

Pregnant women will be scheduled to be seen in the clinic every 4 weeks during their pregnancy and then 1 and 6 weeks following delivery. In addition, pregnant women will be instructed to come to the study clinic for all their medical care and avoid the use of any outside medications. Children will be scheduled to be seen in the clinic at 1, 4, 6, and 8 weeks of age and then every 4 weeks until they reach 52 weeks of age. Parents /guardians will be instructed to bring their children to the study clinic for all medical care and avoid the use of any outside medications. The study clinic will remain open 7 days a week from 8 a.m. to 5 p.m. Pregnant women and children who are not seen on the day of their regularly scheduled visits will be visited at home and instructed to come to the clinic as soon as possible.

Each time a study participant is seen in the clinic a standardized history and physical exam will be performed including temperature, pulse, and blood pressure measurement. Patients who are febrile (tympanic temperature \geq 3 8.0°C) or report history of fever in the past 24 hours will have blood obtained by finger prick for a thick blood smear (in very young children, heel sticks may be substituted for finger pricks). If the thick blood smear is positive, the patient will be diagnosed with malaria. If the thick blood smear is negative, the patient will be managed by study physicians for a non-malarial febrile illness (Section 6.3). If the patient is afebrile and does not report a recent fever, a thick blood smear will not be obtained, except when following routine testing schedules (Section 6.5).

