6.2. Diagnosis and Management of Malaria

Patients found to have malaria based on laboratory confirmation will have a second finger prick for a thin smear (to determine parasite species), hemoglobin measurement using a portable spectrophotometer (HemoCue), and collection of plasma, with residual blood used for testing of an experimental hemozoin-based rapid diagnostic test(MOD) or experimental magnetic levitation-based parasite detection (in children only). All episodes of malaria will be classified as uncomplicated or complicated based on the following criteria:

Uncomplicated malaria (all of the following)

- 1) Fever (> 38.0°C tympanic) or history of fever in the previous 24 hours
- 2) Positive thick blood smear
- 3) Absence of complicated malaria

Complicated malaria (any of the following)

- 1) Evidence of severe malaria (Appendix E) and parasitemia
- 2) Danger signs present in children (Appendix E) and parasitemia

Episodes of malaria will also be classified into the following categories according to the timing of previous malaria episodes for treatment purposes:

- New episodes of malaria will be defined as any first episode or any episode occurring > 14 days after the diagnosis of a previous episode
- 2. Treatment failures will be defined as any of the following:
 - a. Complicated malaria occurring 1-14 days after the diagnosis of a previous episode
 - b. Fever (≥ 38.0°C tympanic) or history of fever in the previous 24 hours with a parasite density ≥ the parasite density of an episode of malaria diagnosed 2 days prior
 - c. Fever (≥ 38.0°C tympanic) or history of fever in the previous 24 hours with a parasite density ≥ 25% of the parasite density of an episode of malaria diagnosed 3 days prior
 - d. Fever (≥ 38.0°C tympanic) or history of fever in the previous 24 hours with a positive thick blood smear of any parasite density occurring 4-14 days after the diagnosis of a previous episode

All patients diagnosed with new episodes of uncomplicated malaria will be prescribed AL, the recommended first-line treatment in Uganda for children and pregnant women in their 2nd or 3rd trimester. Patients with complicated malaria will be prescribed quinine or artesunate according to national malaria treatment guidelines. Children who are less than 4 months of age or weigh <5kg, will be treated with quinine for uncomplicated malaria in accordance with the

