6.3. Management of Non-Malaria Illnesses

Patients who are found to have illnesses other than malaria will receive standard-of-care treatment in the study clinic, according to standardized algorithms, or will be referred to the local hospital. We will avoid the routine use of non-study medications with antimalarial activity, including antifolates (with the exception of assigned chemopreventive regimens), and macrolide antibiotics, when acceptable alternatives are available. In addition, drugs with known risk of torsades de pointes or CYP3A inhibitors (Appendix J and K) will be avoided when prescribing treatment to pregnant women during the time they are taking study drugs. If the study clinician deems treatment with one of the drugs listed on Appendix J or K is required, the clinical management team will be consulted. During follow-up for non-malarial illnesses, blood smears will be done at the discretion of the study physician if the subjects are febrile (tympanic temperature \geq 38.0°C) or report history of fever in the past 24 hours. If the blood smear is positive, the patient will be diagnosed with a new episode of malaria and managed per study protocol.

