Appendix E. WHO Criteria for Severe Malaria and Danger Signs

Criteria for severe malaria

Cerebral malaria - defined as unarousable coma not attributable to any other cause in a patient with falciparum malaria Generalized convulsions (≥ 3 convulsions over 24 hours period) Severe normocytic anemia (Hb < 5 gm/dL) Hypoglycemia Metabolic acidosis with respiratory distress Fluid and electrolyte disturbances Acute renal failure Acute pulmonary edema and adult respiratory distress syndrome (ARDS) Circulatory collapse, shock, septicemia ("algid malaria") Abnormal bleeding Jaundice

Danger signs (in children only)

Less than 3 convulsions over 24 hour period Inability to sit up or stand Vomiting everything Unable to breastfeed or drink Lethargy

Appendix F. Uganda Ministry of Health Guidelines for Routine Care of Pregnant and Postpartum Women, and Newborns

In addition to receiving medical care as described above in the protocol, women and infants enrolled in the study will receive standard routine prenatal and postpartum care according to Uganda Ministry of Health guidelines. These standard procedures are subject to availability at the local health care facilities.

Routine antenatal care. Women enrolled in the study will receive routine care as designated in the Uganda Ministry of Health Guidelines. Routine antenatal care includes screening and treating for syphilis and syndromic management of sexually transmitted infections (STIs). Pregnant women will receive iron and folic acid supplementation. In addition, women will be given multivitamins that will be given once daily. In addition, women receive mebendazole 500mg as a single dose as early as possible after the 1st trimester. Each antenatal visit also includes blood pressure assessment and urine dip stick for proteinuria.

Routine intrapartum/delivery care. Routine delivery care for in-hospital births will include labor management by the midwifery staff and management of obstetrical complications as per Ministry of Health guidelines. Immediate postpartum infant care will include polio and BCG immunization, ophthalmic tetracycline, and vitamin K.

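### The protocol gives no study-clinic smear trigger for a child with an Appendix E danger or severe sign but no fever

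*Combined protocol and SAP*

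**What the plan says.** - **6.1.** A tympanic temperature of 38.0°C or more, or fever reported in the past 24 hours, leads to a thick smear. For everyone else the rule reads: "afebrile and does not report a recent fever, a thick blood smear will not be obtained, except when following routine testing schedules (Section 6.5").
- **6.3.** During follow-up of a non-malarial illness, "blood smears will be done at the discretion of the study physician if the subjects are febrile" or report recent fever. Patients with such illnesses are treated "according to standardized algorithms, or will be referred to the local hospital".
- **6.5.** Blood for a smear is collected at 4-weekly routine visits whatever the temperature, but immediate reading and treatment are ordered only for fever. The rule that non-fever smears do not guide care names pregnant women only.
- **Appendix H.** Infant smears are scheduled every 4 weeks from week 4 to week 52. The week 1 and week 6 visits have none.
- **6.2.** Uncomplicated malaria requires measured or reported fever. Complicated malaria does not. It is "Evidence of severe malaria (Appendix E) and parasitemia", or "Danger signs present in children (Appendix E) and parasitemia".
- **Appendix E.** The danger signs in children are "Less than 3 convulsions over 24 hour period Inability to sit up or stand Vomiting everything Unable to breastfeed or drink Lethargy". The severe criteria include "Severe normocytic anemia (Hb < 5 gm/dL"). The appendix contains no testing instruction.

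**The concern.** The rule for who is tested is narrower than the definition of who has complicated malaria. That definition needs parasitemia, parasitemia needs a smear, and in the protocol text the smear (or its urgent reading) depends on fever. A child with a convulsion, lethargy or inability to feed, and no fever measured or reported, meets half of the definition and has no written route at the study clinic to the other half.

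This is mainly a patient-safety matter. Section 6.1 tells parents to bring children to the study clinic for all care and to avoid outside medication, so the clinic largely controls access to testing. There is a minor data consequence too: complicated malaria in Table 4 counts treated episodes, so an episode never tested for is not counted.

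**Working it through.** **Step 1. Follow a child who has an Appendix E sign but no measured or reported fever.**

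| Where the child is seen | Smear taken? | Read at once? | Source |
|---|---|---|---|
| Unscheduled study-clinic visit | No | n/a | 6.1; 6.3 gives discretion only with fever |
| Routine visit with a scheduled smear | Yes | Not ordered | 6.5 |
| Routine visit at week 1 or 6 | Not scheduled | n/a | Appendix H, 6.1 |
| Referred to hospital | Not specified | Not specified | 6.3 |
| Hospital, after hours | Not specified | Not specified | 6.4 |

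No study-clinic row orders or permits a smear because of the sign itself. The other tests do not fill the gap: Objective 4 and 6.10.4 keep experimental and molecular results out of clinical care.

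**Step 2. Check that the absence of fever from the complicated-malaria definition is consistent.** Appendix E has 16 items (11 severe criteria and 5 danger signs). None requires fever, and none is a trigger in 6.1, 6.3 or 6.5. In 6.2, treatment-failure rules b to d state fever, while rule a (complicated malaria on days 1-14) does not. The protocol therefore recognises complicated malaria without fever.

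**Step 3. Size for Hypothesis 2.** Section 8.4 states 80% power to detect an 18-23% relative difference. The dispersion behind that figure is not given, so I scale it rather than rebuild it. Assume 0-1.5% of infant episodes are missed, equally in both arms, and that information is proportional to the number of episodes. The documents do not supply this range. At 1.5%:

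- 1 - exp(ln(0.82)/√0.985) = 18.1%
- 1 - exp(ln(0.77)/√0.985) = 23.2% (23.15% before rounding)
- power = Φ((1.960 + 0.842) × √0.985 - 1.960) = 79.4%

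**Step 4. Would the same trigger suit women?** This scales the earlier trial to 391 women per arm. Table 9 lists 12 grade 3-4 anemias on 3-dose SP (106 women), and 6 anemias plus 1 hypotension on monthly DP (100 women). Section 1.2 gives parasite prevalence of 40.5% and 5.2%, and 41 malaria episodes on 3-dose SP.

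- Sign events, ceiling: SP 391 × 12/106 = 44.3; DP 391 × 7/100 = 27.4
- Incidental parasitemia among them: SP 44.3 × 0.405 = 17.9; DP 27.4 × 0.052 = 1.4
- Expected SP malaria episodes: 391 × 41/106 = 151.2, so 17.9/151.2 = 11.9%

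These are ceilings. They treat every grade 3-4 anemia as Hb below 5 g/dL, afebrile and unexplained, and they assume that carriage is unrelated to the sign. At the low end, where no anemia meets the cut-off, the SP figure is zero.

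**The case against.** **The gap is narrow.** It needs both no measured fever and no fever reported in 24 hours. Children also have a smear at 4-weekly visits, and nothing bars using that smear for their care. This stands. It is why the frequency is probably low and why, at those visits, the complaint is only about late reading.

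**Other routes exist.** The Schema says "A designated study clinic will be located within Masafu General Hospital", so referral is a short step. After-hours care is outside the 6.1 rule, and the algorithms mentioned in 6.3 may cover danger signs. This stands in part. A reader might infer that staff have no instruction of any kind to test such a child. The documents do not support that, because the algorithms are not included in them. What can be said is that the protocol text contains no trigger, and that no referral or after-hours wording requires a smear. Clinicians would probably test anyway, but at an unscheduled visit that would depart from 6.1 as written.

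**Appendix E is a classification list, not a screening tool.** Its coma criterion presupposes falciparum malaria. Other items need laboratory values; for children, hemoglobin is scheduled only at weeks 12, 28 and 52 and measured when malaria is diagnosed. This stands, so the trigger should use danger signs and clinically evident severe signs only.

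**Why not women too?** A reader might infer that women need the same mandatory trigger. The documents do not support this. From the first study dose to 6 weeks postpartum (6.12), section 6.14 requires grade 3-4 events to be rechecked within 72 hours and alternative causes to be investigated. In Appendix I, hemoglobin below 6.5 g/dL in women is already grade 4. Keeping women's non-fever smears out of care is a deliberate rule. Overriding it could add incidental parasitemia mainly on SP (Step 4) to maternal malaria in Table 3, which counts any treatment. That is a trade-off, not an oversight.

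**Conclusion.** The point holds for children at the study clinic. Sections 6.1, 6.3 and 6.5 tie the smear or its urgent reading to fever, while 6.2 and Appendix E do not tie complicated malaria to fever. A child with a danger or severe sign and no fever may therefore go untested or be treated late.

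The number of such children cannot be derived from the documents. That it is probably low is a judgement based on the broad fever trigger and the nearby hospital. The case for acting rests on possible serious harm to an individual child set against a very small cost.

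A reader might also infer a threat to the trial's conclusions. The documents do not support that. The primary birth outcome does not depend on infant smears. On the assumption in Step 3, the detectable difference for Hypothesis 2 moves from 18-23% to at most 18.1-23.2%, with power of at least 79.4%, which is negligible. This is a cheap safety improvement, not a validity problem.

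**What to change.** Add one sentence to each of 6.1, 6.3 and 6.5. Whatever the temperature, a thick smear is taken, read at once and used for care in a child with:

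- an Appendix E danger sign, with inability to sit or stand meaning a new loss for the child's age; or
- a clinically evident Appendix E severe sign without an obvious non-malarial cause (ordinary neonatal jaundice, for example, would not count).

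Add one case record field marking the episode as afebrile, so that complicated malaria in Table 4 can be reported with and without these episodes. Leave the outcome definitions unchanged. Because 8.2.1 counts malaria treatments, these episodes would also enter infant malaria incidence, and the same field would identify them there.

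For women, at most clarify that the 6.14 work-up may include a smear used for care.

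The cost is a few extra smears, using a test already in place, and possibly a few children treated for incidental parasitemia.

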6.2. Diagnosis and Management of Malaria

Patients found to have malaria based on laboratory confirmation will have a second finger prick for a thin smear (to determine parasite species), hemoglobin measurement using a portable spectrophotometer (HemoCue), and collection of plasma, with residual blood used for testing of an experimental hemozoin-based rapid diagnostic test(MOD) or experimental magnetic levitation-based parasite detection (in children only). All episodes of malaria will be classified as uncomplicated or complicated based on the following criteria:

Uncomplicated malaria (all of the following)

- 1) Fever (> 38.0°C tympanic) or history of fever in the previous 24 hours
- 2) Positive thick blood smear
- 3) Absence of complicated malaria

Complicated malaria (any of the following)

- 1) Evidence of severe malaria (Appendix E) and parasitemia
- 2) Danger signs present in children (Appendix E) and parasitemia

Episodes of malaria will also be classified into the following categories according to the timing of previous malaria episodes for treatment purposes:

- New episodes of malaria will be defined as any first episode or any episode occurring > 14 days after the diagnosis of a previous episode
- 2. Treatment failures will be defined as any of the following:
 - a. Complicated malaria occurring 1-14 days after the diagnosis of a previous episode
 - b. Fever (≥ 38.0°C tympanic) or history of fever in the previous 24 hours with a parasite density ≥ the parasite density of an episode of malaria diagnosed 2 days prior
 - c. Fever (≥ 38.0°C tympanic) or history of fever in the previous 24 hours with a parasite density ≥ 25% of the parasite density of an episode of malaria diagnosed 3 days prior
 - d. Fever (≥ 38.0°C tympanic) or history of fever in the previous 24 hours with a positive thick blood smear of any parasite density occurring 4-14 days after the diagnosis of a previous episode

All patients diagnosed with new episodes of uncomplicated malaria will be prescribed AL, the recommended first-line treatment in Uganda for children and pregnant women in their 2nd or 3rd trimester. Patients with complicated malaria will be prescribed quinine or artesunate according to national malaria treatment guidelines. Children who are less than 4 months of age or weigh <5kg, will be treated with quinine for uncomplicated malaria in accordance with the

Uganda Ministry of Health Guidelines. Patients with treatment failure within 14 days following treatment with AL will be prescribed quinine according to national malaria treatment guidelines. Patients with treatment failure within 14 days following treatment with quinine or artesunate will be treated with quinine plus clindamycin or artesunate.

6.3. Management of Non-Malaria Illnesses

Patients who are found to have illnesses other than malaria will receive standard-of-care treatment in the study clinic, according to standardized algorithms, or will be referred to the local hospital. We will avoid the routine use of non-study medications with antimalarial activity, including antifolates (with the exception of assigned chemopreventive regimens), and macrolide antibiotics, when acceptable alternatives are available. In addition, drugs with known risk of torsades de pointes or CYP3A inhibitors (Appendix J and K) will be avoided when prescribing treatment to pregnant women during the time they are taking study drugs. If the study clinician deems treatment with one of the drugs listed on Appendix J or K is required, the clinical management team will be consulted. During follow-up for non-malarial illnesses, blood smears will be done at the discretion of the study physician if the subjects are febrile (tympanic temperature \geq 38.0°C) or report history of fever in the past 24 hours. If the blood smear is positive, the patient will be diagnosed with a new episode of malaria and managed per study protocol.

6.4. After Hours Visits

Pregnant women will be encouraged to come to Masafu General Hospital maternity ward (open 24 hours a day) and parents/guardians will be encouraged to bring their child to Masafu General Hospital pediatric inpatient ward (open 24 hours a day) when urgent care is needed outside of study clinic hours. Pregnant women or parents/guardians of children will be instructed to inform hospital personnel of their involvement in the study at the time of registration and to visit the study clinic on the following day. If a patient is diagnosed with uncomplicated malaria they will receive treatment from a hospital supply of AL and the doctors will be instructed to refer patients to our study clinic when it opens at 8 am the following day. If a patient is diagnosed with severe malaria, he/she will receive quinine or artesunate following standard treatment guidelines. Patients with non-malarial illnesses will be managed at the discretion of the hospital staff. Upon discharge, patients will receive follow-up at the study clinic as outlined above.

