Women will be enrolled in study on the same day that they provide informed consent for participation in the research study. On the day of enrollment, women will undergo a standardized history and physical examination, and have blood collected by venipuncture (15 cc's) for filter paper sample (for future molecular studies), routine baseline laboratory testing and storage. Routine baseline laboratory testing will consist of a thick blood smear for malaria parasites (will be read later by laboratory technicians not involved in study participants care and will not used for clinical care), RDT testing including a standard RDT using a PTS reader and an experimental RDT (results will not be used for clinical care), qPCR for malaria parasites, CBC and ALT measurement. Women who have history of fever in the previous 24 hours or a temperature \geq 38.0°C (tympanic) will have a thick blood smear read urgently in the study clinic. Women with history of fever in the previous 24 hours or a temperature \geq 38.0°C (tympanic) and a positive blood smear will be diagnosed with malaria and treated as described in section 6.2. At the end of the enrolment visit all study participants will be given a long lasting insecticide treated bed net (ITN) and a household survey appointment will be scheduled within 2 weeks to collect household-level information on the use of bednets, house members, household characteristics, and GPS coordinates (Appendix C).

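### After hours, section 6.4 gives artemether-lumefantrine to every patient with uncomplicated malaria, but section 6.2 requires quinine for children under 4 months or under 5 kg

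*Combined protocol and SAP*

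**What the plan says.** Section 6.2 sets the drug rules for malaria and has no time-of-day limit. The general rule is "All patients diagnosed with new episodes of uncomplicated malaria will be prescribed AL" (AL is artemether-lumefantrine). The exception for the youngest and smallest is "Children who are less than 4 months of age or weigh <5kg, will be treated with quinine for uncomplicated malaria", which the section ties to Ministry of Health guidelines.

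Section 6.2 also sets two rules for treatment failure: "Patients with treatment failure within 14 days following treatment with AL will be prescribed quinine according to national malaria treatment guidelines" and "Patients with treatment failure within 14 days following treatment with quinine or artesunate will be treated with quinine plus clindamycin or artesunate". A failure need not be complicated. Definition 2d requires only fever, or a history of fever in the past day, "with a positive thick blood smear of any parasite density occurring 4-14 days after the diagnosis of a previous episode".

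Section 6.4 covers care outside clinic hours for women and for children, who are directed to the maternity and paediatric wards. Its rule for uncomplicated disease is "If a patient is diagnosed with uncomplicated malaria they will receive treatment from a hospital supply of AL". Doctors are told to refer these patients to the study clinic when it opens at 8 am the following day. For severe malaria, section 6.4 names quinine or artesunate and refers to standard guidelines. That reference is attached to severe malaria only.

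**The concern.** A protocol should give one answer to the question of which drug a given patient receives. Here a young infant with uncomplicated malaria is assigned quinine by one section and AL by another, and the difference depends on whether the child arrives before or after 5 pm.

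Section 6.4 is also the part of the protocol that hospital doctors outside the study team are expected to act on. If they follow it literally, the youngest children start on a drug that section 6.2, and the national guidelines it cites, do not prescribe for them. What is at stake is the interim care of infants and a protocol that staff can follow without contradiction.

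**Working it through.** No statistical calculation applies, so the check sets the two sections side by side.

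| Patient with uncomplicated malaria | Section 6.2 (any hour) | Section 6.4 (after hours) |
|---|---|---|
| New episode, at least 4 months and at least 5 kg | AL | AL |
| Child under 4 months or under 5 kg | Quinine | AL |
| Failure within 14 days of AL | Quinine | AL |
| Failure within 14 days of quinine or artesunate | Quinine plus clindamycin, or artesunate | AL |

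**Are the affected children in the trial?** Yes. Section 3 follows all children from birth to 12 months, and section 6.4 tells parents to use the paediatric ward after hours. The age rule alone spans 4/12, or one third, of each child's planned follow-up, and the weight rule can extend it.

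**Does section 6.4 point back to section 6.2?** Other places where malaria is diagnosed do point back to the main rules. Section 4.4 says a febrile woman with a "positive blood smear will be diagnosed with malaria and treated as described in section 6.2". Section 6.5 cites section 6.2 for routine visits. Section 6.3 says "the patient will be diagnosed with a new episode of malaria and managed per study protocol". Section 6.4 names a drug and has no such link.

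**Can the ward apply the section 6.2 rules?** Age and weight can be checked at the bedside, so the infant rule is a clean mismatch. For failures, definition 2d needs no earlier parasite density, but it does need the date of the last episode, and choosing the drug needs the previous treatment. The documents do not say that the ward has either. Definitions 2b and 2c (days 2 and 3) also need an earlier density. Leaving those to the clinic is reasonable.

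**How long does the mismatch last?** The clinic is open from 8 am to 5 pm, so the closed period is (24 − 17) + 8 = 15 hours. If the referral means the next opening, 15 hours is the longest wait. Section 6.1 requires a history and physical examination at every clinic visit. Section 6.4 does not say that the drug is checked against section 6.2 at that visit.

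**Does the infant outcome depend on the drug?** Section 8.2.1 counts a malaria treatment only if no other treatment was given in the previous 14 days, whichever drug is used. A change from AL to quinine the next day would not add an episode.

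**The case against.** The best reply is that section 6.4 concerns logistics: where to go, whose stock is used, and when to attend the clinic. Section 6.2 itself opens with a general rule for all new episodes and then makes an exception for small infants. Nobody reads that as a contradiction, because the specific sentence limits the general one. The same convention could be applied to section 6.4, which nowhere claims to replace section 6.2.

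That reading works within section 6.2, where rule and exception stand together. It does not cure section 6.4, which is a separate instruction for hospital doctors, names only AL for uncomplicated disease, and sends the patient to the clinic after AL has been given.

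Two further points stand in part. Ward doctors may know the national guidelines that section 6.2 invokes for infants and for failure after AL, and would then give quinine anyway. That lowers the practical risk, but such a doctor departs from section 6.4 as written. The next-day visit also limits how long a child would stay on AL.

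The objection is strongest on treatment failures. A reader might infer that this mismatch is as clear as the one for infants. The documents do not support that, because the ward may not hold the episode history. Interim AL with reclassification at the clinic the next day is a reasonable arrangement for those patients.

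**Conclusion.** The inconsistency is real and minor. For children under 4 months or under 5 kg, section 6.4 as written assigns AL where section 6.2 requires quinine. For uncomplicated failures on days 4 to 14 there is a secondary mismatch that depends on history the ward may not have. The effect is limited to interim treatment, on the assumption that patients attend the next day as instructed and that the clinic then applies section 6.2.

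Two stronger readings should be resisted. A reader might infer that the infant malaria comparison is biased. The documents do not support that: the after-hours rule is the same in both blinded arms, and the outcome definition does not depend on the drug used. A reader might also take the one-third of follow-up, or the 15 closed hours, as a measure of how many children are affected. Those figures describe calendar and clock time only. The documents give no after-hours attendance rate and no malaria incidence under 4 months. The 3 to 5 episodes per person-year in section 8.4 is an assumption for the whole first year in the SP arm. The number affected therefore cannot be estimated.

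**What to change.** Amend section 6.4 to say that after-hours treatment of uncomplicated malaria follows section 6.2. Specifically:

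- before giving AL, the ward checks age and weight, and gives quinine to children under 4 months or under 5 kg;
- where possible, the ward asks about malaria treatment in the previous 14 days (date and drug) and applies the treatment-failure rules if the answer is clear;
- at the next-day visit the study clinic confirms the drug against section 6.2, including the density-based failure definitions, and changes it if needed.

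The cost is a short amendment and an instruction sheet for the ward. Section 10.10 requires ethics review of any modification by all participating institutions, so this is more than an editorial change. Section 6.4 already names quinine and artesunate for severe malaria, so no new drug is needed for the infant rule. Clindamycin would be needed only if that option were chosen over artesunate for failure after quinine or artesunate. Design, blinding, endpoints and sample size are unchanged.
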